Visit Name	Safety Follow-up Visit 1	Safety Follow-up Visit 2	Additional Follow-up Visits ¹	End of Safety Follow-up Visit			
Days	EOS + 3 Months ±14	EOS + 6 Months ±14	Every 3 months ±14 after Safety Follow-up Visit 2	Early discontinuation	Completion ⁶		
MS Relapse	X	Х	X	Х			
EDSS	Х	Х	X	Х			
Physical Exam (including weight)	Χ	Х	X	X			
Vital Signs	Х	X	X	X			
Routine lab samples including urine	X	X	X	×			
Sample for CD19+ B-cells (all sites)	Х	Х	х	х			
Sample for B-cell and T-cell subset testing (US sites only)	X	Х	Х	х			
Total IgG, IgM levels	Х	Х	X	Х			
Neurofilament and CCI Sampling	X	Х	Х	х			
Urine Pregnancy Test ²	X	Х		X ⁷			
Contraception Status ^{3,4}	Х	Х		X ⁷			
Concomitant medications ⁵	Х	Х	X	Х	Х		
Adverse Events	Х	Х	X	X	Х		
Safety Follow-up Subject Disposition				X	Х		

X Assessment to be recorded in the clinical database or received electronically from a vendor

¹ As needed for the subjects requiring prolonged Immunoglobulin (IgG and IgM) monitoring; refer to Section 9.2.1.

² Pregnancy test is conducted on female subjects only. Urine pregnancy tests will be conducted at all scheduled visits as indicated in Table 8-2. Monthly urine pregnancy tests will be conducted at home between site visits. The subject must contact the Investigator immediately in the case of a positive test for confirmatory testing at the Investigator's discretion.

³ Subject's contraception status must be reviewed and documented to ensure method of contraception continues to be appropriate per protocol requirement for highly effective contraception.

⁴ Assessments captured as source data

5 Including corticosteroids used to treat MS relapse; any newly started MS treatment as applicable.

6 For subjects completing Safety Follow-up, the End of Safety Follow-up visit will be performed by telephone contact (after the central laboratory results have confirmed that IgG and IgM results are ≥ screening or LLN) to inform the subject that his or her participation in the Safety Follow-up has ended; the disposition form will be completed at that time and the AE and concomitant medications eCRFs will be updated if necessary to record any new or worsening events or medication changes since the last clinic visit. Please refer to Section 9.2.1.

7 To be performed only if less than 6 months after stopping study medication

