9.2.1 Safety Follow-up

Subjects moving into the Safety Follow-up period, as described in Section 3, will continue for 6 months post last dose of ofatumumab treatment. A shorter follow-up time is acceptable if subjects select a different MS treatment during this period as presented below.

At the EOS + M6 Visit:

- If a subject has IgG and IgM results ≥ screening or LLN, this visit shall be considered final clinic visit for the subject. The End of Safety Follow-up visit will be performed by telephone contact to inform the subject that his or her participation in Safety Follow-up has ended; the disposition form will be completed at that time and the AE and concomitant medications eCRF will be updated if necessary to record any new or worsening events or medication changes since the last clinic visit.
- If a subject has either IgG or IgM results < screening or LLN, Safety Follow-up clinic visits will continue on a plus 3 monthly basis until both IgG and IgM values are ≥ screening or LLN. The End of Safety Follow-up visit will be performed by telephone contact to inform the subject that his or her participation in Safety Follow-up has ended; the disposition form will be completed at that time and the AE and concomitant medications eCRFs will be updated if necessary to record any new or worsening events or medication changes since the last clinic visit; refer to Table 8-2.

• Note: All IgG and IgM results are required to be confirmed by a Central Laboratory result. IgG/IgM assessments performed by a local laboratory under the Public Health Emergency mitigation procedures defined in Section 8.4.5 are not to be used to determine if the subject has met the criterion for their last immunoglobulin follow-up visit. During a Public Health Emergency, subjects should continue to be monitored until it is feasible and safe to schedule a clinic visit to obtain a sample for central laboratory evaluation unless Last Subject Last Visit (LSLV) has already been declared for the study. In such circumstances, please follow the guidance presented below.

Patients starting a different MS treatment during Safety Follow-up:

• During Safety Follow-up subjects may receive any DMT for the treatment of MS as the investigator deems necessary. Prior to starting the MS DMT, subjects will be brought in for their final Safety Follow-up visit. This visit will be the End of Safety Follow-up visit for the subject and the disposition page will be completed at this time.

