The study is envisioned to end when the last subject who entered Safety Follow-up completes his or her EOS + M6 clinic visit and the End of Safety Follow-up telephone contact visit defined as LSLV. It is possible that a small subset of subjects may still have low immunoglobulin levels and therefore ongoing in Safety Follow-up as the LSLV date approaches. Study follow-up for these subjects will be truncated so that their final visit will be performed on or prior to the scheduled LSLV date for the study. Subsequent follow-up immunoglobulin monitoring for these subjects, and last subject if necessary, will be performed outside of the study at the discretion of the treatment investigators and documented in subject's medical records only.

10 Safety monitoring and reporting

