			For safety analysis, add more separate summaries of TEAEs, add infection as another AESI, keep same IRR analyses as compared to ASCLEPIOS, add IgG, IgM, lymphocyte and neutrophils analyses by last prior DMT, add treatment discontinuation or interruption by	Section 2.9
			IgG and IgM ≥LLN vs. < LLN Exclude PROs and digital endpoints from CSR	Section 2.12 and 2.14

Date	Time point	Reason for update	Outcome for update	Section and title impacted (Current)
			For exploratory analyses, add 6mCDW and also by last prior DMT, add 6mCCD, add T1 and T2 lesions by last prior DMT, add NEDA-3 and also by last prior DMT, add proportion of subjects without MRI activity, add color and also by last prior DMT, add T25FW, 9HPT and LCVA, add NfL and also by last prior DMT. Add a section of Interim analysis	Section 2.15
			Update the latest calculation of sample size, aligning with the latest protocol and sample size document Specify the change to protocol specified	Section 2.16 Section 3
			analyses Document the PD which causes data/sample	Section 4
			to be excluded from final analyses	Section 5.5
8- July- 2020	Prior to DB lock	Creation of final version	N/A - First version	NA
29- Apr- 2021	SAP amendment	Protocol amendment	Updated safety follow up details based on protocol amendment; safety follow up post study drug discontinuation is reduced to 6 months instead of 9 months	Section 1.1 Study design
		Protocol amendment	Changed NEDA-4 to NEDA-3 Removed endpoint percentage change from baseline in brain volume	Section 1.2 Study objectives and endpoints Table 2-2 Section 2.3.3 Section 2.14 Other exploratory analyses
		Protocol amendment	Added summary of missed doses	Section 2.4
		Protocol amendment	Added pandemic impact analysis for efficacy; Added analysis to assess impact of missed doses on primary endpoint	Section 2.5.4 Sensitivity / supplementary analyses
		Protocol amendment	Added pandemic impact analysis for safety	Section 2.9 Safety analyses
		Protocol amendment	Added bar plot for injection related reactions and symptoms	Section 2.9.1.1.1 Injection reaction related AEs
		Protocol amendment	Added analysis to assess impact of missed doses on special labs parameters	Section 2.9.3.1
		Protocol amendment	Removed this section as this will be not used for CSR	Section 2.9.5 Safety evaluation during safety follow up

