2.1.2.2 Visit windows after study drug discontinuation

For summaries of data collected after study drug discontinuation, data from both treatment epoch and safety follow-up epoch will be considered. Participants who prematurely discontinue the study drug will be required to have their EOS visit as soon as possible and enter into the SFU according to the assessment schedule in protocol Table 8-2. In the SFU, all assessments are relative to EOS visit. Day 1 will be the first day after EOS visit. The visit window definitions for SFU Visit 1 and Visit 2 are provided in Table 2-11. The SFU Visit 2 will be the last clinic visit and the end of SFU Visit will be performed by telephone contact. Additional SFU Visit will be required if participants have either IgG or IgM < screening or LLN, and they will be performed outside of the study.

Table 2-11 Visit-windows after study drug discontinuation

Visit-window	Start day	Target day	End day
SFU Visit 1	1	84	126
SFU Visit 2	127	168	210

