2.9.3.1 Other special lab results

Other non-routine laboratory data include B-cell counts, total IgG, total IgM, and other biomarkers such as neurofilaments. All data will be listed appropriately.

The B-cell counts, total IgG, total IgM, neurofilaments, lymphocytes and neutrophils will be summarized using descriptive statistics by visit-window. IgG, IgM, lymphocytes and neutrophils will also be summarized by visit-window and last prior DMT.

In addition, number and percentage of subjects with B-cells < the lower limit of normal (LLN) or < their baseline value (i.e., B-cell depleted) will be presented by visit window. For subjects who entered the safety follow-up, number and percentage of subjects with B-cell recovery (above LLN) will be summarized by SFU visit-window.

Number and percentage of subjects with IgG and IgM below LLN and meet the notable low level criteria in IgG or IgM by visit window will be provided. IgG and IgM will also be summarized by visit window and last prior DMT. A notably low IgG level is defined as a level that is ≤ 4.5 g/L (20% below LLN) and ≤ 0.36 g/L (10% below LLN) for IgM. LLN is 5.65 g/L for IgG and 0.4 g/L for IgM. For subjects who had IgG or IgM below LLN at the time of entering SFU, number and percentage of subjects with IgG or IgM recovery (above LLN) will be summarized by SFU visit-window.

Number and percentage of subjects with lymphocytes and neutrophils below LLN and meet the notable abnormalities by visit window will be provided. Lymphocytes and neutrophils will also be summarized by visit window and last prior DMT. Notable abnormalities for lymphocytes and neutrophils are listed in Table 2-12.

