2.9.4.3 Treatment discontinuation or interruption due to lack of efficacy or tolerability

The proportion of subjects discontinuing treatment or having treatment interruption due to insufficient effectiveness (lack of efficacy) or tolerability/safety reasons will be provided. On treatment disposition CRF page, reason for discontinuation "Lack of efficacy" and "Adverse events" will be selected to provide this summary. In addition, treatment discontinuation or interruption due to lack of efficacy or safety will also be summarized by participants who have IgG < LLN at any point post-baseline vs participants who have $IgG \ge LLN$ at any point post-baseline. Same analysis will be repeated by IgM.

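### The IgG and IgM groups in the SAP's discontinuation table overlap, because both are defined by a value occurring at any time after baseline

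*SAP*

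**What the plan says.** SAP 2.9.4.3 summarises the proportion of participants who stop or interrupt treatment for lack of efficacy or for safety reasons. Discontinuation for these reasons is a secondary endpoint (Protocol Table 2-1, SAP 2.8). The section then breaks the summary down by immunoglobulin status, comparing "participants who have IgG < LLN at any point post-baseline vs participants who have" an IgG at or above LLN. The second group carries the same any-time qualifier as the first, and the analysis is repeated for IgM. Nothing in that section or in SAP 2.9.3.1 says where a participant with both kinds of value belongs.

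The SAP's document history, cited here only for intent, describes the split as "IgG and IgM ≥LLN vs. < LLN".

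On follow-up, SAP 2.1.2.2 calls safety follow-up (SFU) Visit 2 the last clinic visit. It says of additional visits for low IgG or IgM: "and they will be performed outside of the study". In the protocol, Table 8-2 has a column for such visits, footnoted "As needed for the subjects requiring prolonged Immunoglobulin (IgG and IgM) monitoring", with IgG/IgM marked X. The key to X reads "Assessment to be recorded in the clinical database or received electronically from a vendor". Section 9.2.1 says that "Safety Follow-up clinic visits will continue on a plus 3 monthly basis until both IgG and IgM values are" back to the screening or LLN criterion.

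**The concern.** A two-column contrast needs each participant in one column. Here the low column means ever low, but the other column, read literally, means ever not low. A participant who dips below LLN once and is otherwise normal appears in both. The second column then contains many of the people it is supposed to be compared with, the column totals exceed the number of participants, and any difference between the columns is pulled towards zero.

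At stake is the readability of one descriptive table that relates immunoglobulin level to stopping treatment. No test, error rate or sample size depends on it.

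**Working it through.** The plan gives no figure for this table, so there is none to reproduce. The definitions can be checked directly.

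**Overlap by pattern.** SAP Table 2-7 gives five post-baseline IgG/IgM windows (Weeks 4, 24, 48, 72, 96). Code each as low or not low: 2^5 = 32 patterns.

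- At least one low: 32 − 1 = 31.
- At least one not low: 32 − 1 = 31.
- Both: 32 − 2 = 30.

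Only the all-low and the all-not-low patterns have a unique column. If the second group requires every value to be at or above LLN, the counts become 31, 1 and 0 in both. These are counts of patterns, not probabilities. A participant with a single post-baseline sample cannot be in both groups, and one with none is in neither.

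**Illustrative size.** Inputs: N = 555 (Protocol Section 5). Assumed, because the documents give no values: share ever low p = 10% or 30%; share s of these who also have a non-low value = 50% or 100%; stopping rate 15% in the ever-low and 8% in the never-low; everyone has a post-baseline value.

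- Counted twice = N·p·s.
- Column total = N + N·p·s.
- Rate in the ≥ LLN column = [N(1−p)·0.08 + N·p·s·0.15] / [N(1−p) + N·p·s].

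| p | s | In both | Column total (% of N) | Rate, ≥ LLN column | Difference from 15% |
|---|---|---|---|---|---|
| 10% | 50% | 27.75 | 582.75 (105%) | 8.37% | 6.63 points |
| 10% | 100% | 55.5 | 610.5 (110%) | 8.70% | 6.30 points |
| 30% | 50% | 83.25 | 638.25 (115%) | 9.24% | 5.76 points |
| 30% | 100% | 166.5 | 721.5 (130%) | 10.10% | 4.90 points |

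With exclusive groups the difference is 15 − 8 = 7.0 points, so the dilution is 0.4 to 2.1 points. The standard error of the exclusive difference is √(0.15·0.85/55.5 + 0.08·0.92/499.5) = 4.9 points at p = 10%, and √(0.15·0.85/166.5 + 0.08·0.92/388.5) = 3.1 points at p = 30%. The dilution is below the standard error throughout.

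**Follow-up wording.** SAP 2.1.2.2 puts every additional visit outside the study. Protocol 9.2.1 keeps them in the study up to last subject last visit (LSLV): "Study follow-up for these subjects will be truncated so that their final visit will be performed on or prior to the scheduled LSLV date". It places only later monitoring outside. SAP 2.9.3.1 states that "number and percentage of subjects with IgG or IgM recovery (above LLN) will be summarized by SFU visit-window". Table 2-11 has windows for SFU Visits 1 and 2 only, ending at Day 210. An additional visit at EOS + 9 months, taken as three 84-day quarters less the 14-day allowance, falls at Day 3 × 84 − 14 = 238 or later, so it has no window.

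**The case against.** The best defence is that the intent is clear. The comparison is framed as one group versus another, the document history describes a simple split, and a sympathetic reader may take the second any-time qualifier to mean at every point. That the intent is recoverable stands. It does not settle the matter, because the operative text uses one qualifier for both groups and a program following it literally produces overlapping columns.

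It is also fair that the effect is small. On the illustrative figures the dilution is below sampling error, and every share and rate behind those figures is assumed. A reader might infer that the table would be seriously misleading, or that the trial's conclusions are touched; the documents support neither.

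Simply replacing any with all would not finish the job. Participants with no post-baseline value, who may be early stoppers, would be unassigned or would fall into the second group by default.

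On follow-up, a reader might infer that recoveries after SFU Visit 2 are lost, or that a known number of patients is affected. Neither follows. SAP 2.9.3.1 already says these data will be listed, and omitting a later window is a permissible choice. Protocol 9.2.1 expects only a few participants to be still low near LSLV, but that is not everyone still low at EOS + 6 months. The recovery table also covers only those below LLN when they enter follow-up, whereas the protocol trigger for extra visits also refers to the screening value. No count can be derived. The SAP's text on data cut-offs and on changes from the protocol is not visible, so it cannot be checked for a further rule.

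**Conclusion.** The grouping in SAP 2.9.4.3 is defective as written, for IgG and for IgM. Anyone with mixed post-baseline values is counted on both sides, and the ≥ LLN column is not a never-low comparator. That conclusion rests on the text alone. Its size does not: double counting of 28–167 participants and a dilution of 0.4–2.1 points hold only under the assumed shares and stopping rates.

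Severity is minor. Even with exclusive groups the contrast would not be causal, because participants treated for longer have more samples and so more chances of a low value.

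The follow-up statement in SAP 2.1.2.2 is a secondary wording inconsistency with Protocol Table 8-2 and Section 9.2.1. It is not a separate error in results.

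**What to change.** In SAP 2.9.4.3, define the groups separately for IgG and IgM as:

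- below LLN at one or more post-baseline assessments;
- at or above LLN at all post-baseline assessments, with at least one available;
- no post-baseline value, shown in its own row.

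Every participant in the safety set then has one place. A footnote should say that the comparison is descriptive and depends on the number of samples per participant.

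In SAP 2.1.2.2, reconcile the sentence on additional visits with Protocol Table 8-2 and Section 9.2.1, and state whether results from in-study additional visits are only listed or also summarised. A later window would hold few, selected participants, so listing alone is defensible.

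The cost is SAP wording and a small programming change. No new data are needed.

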2.9.4.4 Suicidality evaluations

The eCSSRS data will be mapped to Columbia Classification Algorithm for Suicide assessment (C-CASA) as per FDA guidance on suicidality. The proportion of subjects who have completed suicide, suicide attempt, and preparatory actions toward imminent suicidal behavior, suicidal ideation, and self-injurious behavior without suicidal intent as per the C-CASA scale during the study (safety data cutoff applies) at any time post baseline will be summarized.

The Columbia Suicide Severity Rating Scale (C-SSRS) questionnaire will be administered via electronic device (eC-SSRS). However, as per internal Novartis guidelines, a CRF page 'Supplemental Data for Suicidal Ideation and Behavior Categories' is also used as an unplanned/unscheduled visit for those cases when the subject did not conduct the phone interview because, e.g. the subject was hospitalized and unable to conduct the interview or the subject refused to conduct the interview/withdrew from the study and external information on suicidal ideation and behavior (SIB) is required. In such cases, SIB information will still be collected from external parties (spouse, caregiver, nurse, investigator, etc.) through means of this CRF page. Further, for deaths due to suicide, the site should fill out the Supplemental Data CRF ("completed suicide" tick box) to ensure accurate reporting of such cases. When reporting the SIB data, data from both sources (eC-SSRS and Supplemental CRF) will be used in a pooled manner and no distinction will be made between the two.

Table 2-15 Standard SIB events as categorized by C-SSRS

Category number	C-SSRS category
Suicidal Ideation	
1	Wish to be dead
2	Non-specific active suicidal thoughts
3	Active suicidal ideation with any methods (not plan) without intent to act

	4	Active suicidal ideation with some intent to act, without specific plan		
	5	Active suicidal ideation with specific plan and intent		
Suic	idal behavior			
	6	Preparatory acts or behavior		
	7	Aborted attempt		
	8	Interrupted attempt		
	9	Actual attempt		
	10	Completed suicide		
Self-	Self-injurious behavior, without suicidal intent			
	11	Non-suicidal self-injurious behavior		

2.10 Pharmacokinetic endpoints

Not Applicable.

2.11 PD and PK/PD analyses

Not Applicable.

2.12 Patient-reported outcomes

All the Patient-reported outcomes CCI will be analyzed as part of exploratory endpoints outside of CSR separately.

2.13 Digital endpoints

All digital endpoints outside of CSR separately. will be analyzed as part of exploratory

2.14 Other Exploratory analyses

Following exploratory endpoints will be analyzed as part of CSR based on FAS population.

2.14.1 6-month Confirmed Disability Worsening (6mCDW)

A 6-month confirmed disability worsening (6mCDW) is defined as an increase from baseline in EDSS sustained for at least 6 months. This means that after a scheduled or unscheduled visit at which the participant fulfills the disability worsening criterion as defined in Table 2-16, all EDSS assessments (scheduled or unscheduled) need to also fulfill the worsening criteria until the worsening ("the event") can be confirmed at the first scheduled visit that occurs in the absence of (confirmed or unconfirmed) relapse 6 months/166 days after the onset of the worsening, or later.

In the time to event (6mCDW) analysis, time will be calculated as (the date of EDSS assessment at onset of the event – date of first administration of study drug+1) for patients with the events. Censoring occurs in those participants who did not experience an event up to the analysis cutoff date (i.e. end of treatment epoch date), this includes participants who had a "tentative" disability worsening that could not be confirmed due to an early discontinuation or any another reason.

The censoring time is calculated as (the date of last EDSS assessment up to analysis cutoff date – date of first administration of study drug+1). Additional details are provided in footnote of Table 2-16.

Table 2-16 Criterion for disability worsening based on change in EDSS score

Total EDSS at baseline*	"Disability worsening" criterion
0	≥ +1.5
0.5 to 5	≥ +1
≥5.5	≥ +0.5

A 6-month confirmed disability worsening can have an onset at any scheduled or unscheduled visit if the disability worsening criterion is met. A disability worsening event can only be confirmed at a scheduled visit in the absence of (confirmed or unconfirmed) relapse if, over a period of 6 months (≥166 days=6*30-14 [visit window]) time interval, all assessments meet the worsening criterion.

If a participant dies due to MS (EDSS=10 at any time), it will be considered a confirmed disability worsening regardless of the baseline EDSS or the change in EDSS. The time will be calculated as (date of EDSS assessment at a tentative onset of the event – date of first administration of study drug+1) or (date of death – date of first administration of study drug + 1) if a tentative onset date does not exist. Note: Death for other reasons than MS (i.e. not EDSS=10) will not be considered a disability worsening.

*Baseline EDSS is defined as the last EDSS assessment prior to the first dose of study medication (protocol inclusion criterion is EDSS 0-4 at screening)

For statistical analysis, Kaplan-Meier curves (and/or cumulative incidence plots) will be provided to present the time-dependent cumulative probability of participants reaching 6mCDW. Kaplan-Meier (KM) estimates will be calculated for the study with 95% confidence intervals. Separate Kaplan-Meier curves and estimates will also be calculated with 95% confidence intervals for last prior DMT subgroup (fumarates vs. fingolimod).

2.14.2 6-month Confirmed Cognitive Decline (6mCCD)

A 6-month confirmed cognitive decline (6mCCD) is defined as at least a 4-point worsening on score sustained for at least 6 months. Event rate by time interval (0-12 months, 12-24 months) will be provided to participants reaching 6mCCD. Cumulative event rate will be calculated with 95% confidence intervals.

